## 11. OTHER EFFICACY ASSESSMENTS

### 11.1. Patient-Reported Outcomes

#### 11.1.1. EXACT®

The EXACT PRO was developed and qualified for use in characterizing COPD clinical endpoints ([Jones, 2011\[2\]](#); [Leidy, 2010\[6\]](#); [Leidy, 2011\[5\]](#); [US FDA, 2013\[15\]](#)). Several of the concepts assessed by the EXACT are relevant to characterizing the symptomatic phenomena expected within bronchiectasis. These include, but are not limited to, dyspnea and fatigue. The EXACT total score measures acute, sustained, and worsening signs and symptoms exceeding subject-specific expected variability. The EXACT PRO is composed of 14 items from which a total score is generated. Domains assessed by the EXACT PRO include dyspnea, cough and sputum production, chest symptoms, difficulty expectorating, fatigue, sleep disturbance, and fear or concern.

If missing values occur for individual items, the scores cannot be calculated and should be set to missing.

#### EXACT Total Score

A raw summed score is derived as the sum of the item-level raw scores of the 14 EXACT items (see [Appendix C](#)).

For each raw summed score, the corresponding EXACT total score is assigned (see [Table 4](#)) The EXACT total score has a theoretical range of 0 to 100, with higher values indicating a more severe condition. Negative change from baseline indicates improvement (post therapy score – baseline score < 0).

For the purpose of analysis, if an EXACT total score is 0 it will be changed to missing. This scoring rule is based on previous validation work demonstrating that moderate-to-severe COPD patients will experience symptom(s) each day, and a score of 0 on all 14 EXACT items is likely to represent a situation where in order to complete the diary quickly, the respondent did not accurately report their daily symptom(s).

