1.3.2. Treatment and Duration of Exposure

Patients to be evaluated in this study have mild disease and have not received treatment for their current MAC lung infection. The design and treatment have been extensively discussed and agreed with a global steering committee of experts experienced in the management of NTM pulmonary disease and with regulatory agencies. Subjects will be randomized to ALIS + background regimen or ELC + background regimen. Note that background regimen in this study is defined as AZI+ETH per randomized treatment. Treatment will be administered continuously for 6 months followed by 1 month off treatment period with a final EOS evaluation at Month 7. It was agreed upon with the FDA that an active control that is also used in clinical practice would be used in the study.

Based on extensive consultations with medical experts, in this population of newly diagnosed MAC patients with non-cavitary lung disease, treatment with 2 drug oral regimen, specifically azithromycin and ethambutol has been confirmed as acceptable. This macrolide-based regimen is currently prescribed in clinical practice, and keeping the background regimen simple and tolerable will help subjects remain in the study. The regimen excludes rifabutin or rifampin which are associated with well-described side effects that affect patients with MAC lung disease and patient tolerability for regimens that include one of these 2 drugs. In addition, the chosen companion drugs to ALIS can also be considered to contribute to the therapeutic success by virtue of their ability to prevent overgrowth of organisms that may develop resistance to individual agents in the regimen during the course of treatment.

As stated in both the BTS and ATS/ERS/ESCMID/IDSA guidelines, a 2-drug regimen including a macrolide and ethambutol is the regimen with the fewest possible drugs for treating MAC. Data recently published subsequent to the release of the global guidelines show that the 2-drug regimen of azithromycin and ethambutol may be an option for the treatment of non-cavitary MAC lung disease: 76% of patients were able to achieve sputum culture conversion after 12 months of treatment, and none of those who failed to culture convert developed macrolide resistance (Moon et al., 2019). Ethambutol is likely the key companion drug for preventing the

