#### RS-Total Score

The RS-Total score is the sum of the individual raw item scores (item 1 to item 11) of the EXACT PRO (see [Appendix C](#)). Scores range from 0 to 40. Higher values indicate a more severe condition. Negative change from baseline indicates improvement (post therapy score – baseline score < 0).

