#### E-RS: COPD Subscale Scores

For each subscale, the sum of the item-level scores across the items comprising the scale is calculated.

- RS-Breathlessness: Items 7, 8, 9, 10, 11 (score range 0–17)
- RS-Cough & Sputum: Items 2, 3, 4 (score range 0–11)
- RS-Chest Symptoms: Items 1, 5, 6 (score range 0–12)

If the EXACT total score is 0, the RS-Total Score and Subscale Scores will be set to missing.

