#### 11.1.5. Analysis of PRO Scores

PRO scores will summarize available data. Summaries will be presented by treatment group and by timepoint, as follows. Summaries will include:

1. Basic statistics of actual values and change from baseline to all protocol-specified timepoints.
2. LS-mean of change from baseline to Month 7, differences of LS-mean changes from baseline (ALIS + background regimen – ELC + background regimen) estimates and corresponding 95% CIs derived from ANCOVA model. The ANCOVA model will include change from baseline as response variable and treatment, baseline value, and history of MAC lung infection (initial or subsequent) as independent variables.

The following PRO scores will be summarized:

EXACT (see Section 11.1.1)

- EXACT Total score
- Breathlessness domain score
- Cough & Sputum domain score
- Chest Symptoms domain score

EXACT-RS (see Section 11.1.2)

- RS-Total score
- RS-Breathlessness subscale score

- RS-Cough & Sputum subscale score
- RS-Chest Symptoms subscale score

SGRQ (see [Section 11.1.3](#))

- Total score
- Symptom component score
- Activity component score
- Impact component score

FACIT – Fatigue Scale (see [Section 11.1.4](#))

- Fatigue subscale score

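### At Month 7 an all-zero EXACT form is scored as missing on a COPD rationale, which removes fully symptom-free subjects from the EXACT total and E-RS comparisons

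*SAP*

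**What the plan says.** SAP Section 11.1.1 states: "For the purpose of analysis, if an EXACT total score is 0 it will be changed to missing". Its justification is: "This scoring rule is based on previous validation work demonstrating that moderate-to-severe COPD patients will experience symptom(s) each day". From this the SAP infers that an all-zero response probably comes from a respondent hurrying through the diary.

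Section 11.1.2 carries the rule to the respiratory subset: "If the EXACT total score is 0, the RS-Total Score and Subscale Scores will be set to missing".

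On both instruments 0 is the best end. For EXACT, "The EXACT total score has a theoretical range of 0 to 100, with higher values indicating a more severe condition". For the E-RS total, "Scores range from 0 to 40", again with higher values worse.

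The analysis is set in SAP Section 11.1.5: "PRO scores will summarize available data". It consists of summaries by timepoint and an ANCOVA of change from baseline to Month 7. No imputation and no zeros-retained sensitivity analysis is described for these scores.

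On the population, Protocol Section 1.3.2 says: "Patients to be evaluated in this study have mild disease and have not received treatment for their current MAC lung infection". Protocol Table 4 schedules EXACT and EXACT-RS at Screening, Baseline and Month 7 only. Protocol Section 6.1 has the PROs completed on a tablet, ahead of the other assessments apart from sputum collection.

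**The concern.** The rule rests on two premises: that patients of this kind have symptoms every day, and that a hurried diary entry is the likely explanation for a zero. Neither is argued for this trial. COPD is named in the protocol only as an example of underlying lung disease, the MAC infection is described as mild, and the form is completed at a few scheduled visits. The items ask mainly about the current day (SAP Appendix C). After six months of treatment and one month off it, a day with no symptoms is a plausible true answer.

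If so, the rule makes missingness depend on the outcome. A subject whose symptoms resolve fully is dropped, while one who keeps a single slight symptom is kept. If full resolution is commoner in one arm, that arm loses more of its best results and part of its advantage disappears from the EXACT total and E-RS comparisons.

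**Working it through.** **1. Reproduce the stated score ranges.** Inputs are the item maxima in SAP Appendix C, items 1 to 14: 4, 4, 3, 4, 4, 4, 4, 3, 4, 3, 3, 4, 4, 3.

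- All 14 items sum to 51, the top raw score in SAP Table 4.
- Items 1 to 11 sum to 40, the stated E-RS maximum.
- E-RS Breathlessness (items 7 to 11): 4 + 3 + 4 + 3 + 3 = 17. Cough & Sputum (2, 3, 4): 4 + 3 + 4 = 11. Chest Symptoms (1, 5, 6): 4 + 4 + 4 = 12. All agree with Section 11.1.2.

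**2. What the rule removes.** Table 4 maps raw 0 to 0 and raw 1 to 8. An EXACT total of 0 therefore means that all 14 items are 0, and under the rule the best analysable total is 8. For E-RS, only records with all 14 items at 0 are removed. An E-RS total of 0 stays if item 12 (tired or weak), 13 (sleep) or 14 (worry) is above 0. Whether a best-possible respiratory score counts thus depends on three items outside that scale.

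**3. Same items, two treatments.**

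| Score | Items | All-zero form |
|---|---|---|
| EXACT Breathlessness domain | 7–11 | no zero rule stated; scored 0 |
| E-RS Breathlessness | 7–11 | missing |
| EXACT Chest Symptoms domain | 1, 5, 6 | no zero rule stated; scored 0 |
| E-RS Chest Symptoms | 1, 5, 6 | missing |

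Section 11.1.5 reports all four, so the same answers could be tabulated with different numbers of subjects.

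**4. Effect on the Month 7 contrast.** Let p be the share of true all-zero forms in an arm and m the mean EXACT total among the other subjects.

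- Arm mean with zeros kept: (1 − p) × m
- Arm mean under the rule: m
- Overstatement of the arm mean: p × m
- Shift in ALIS minus ELC when zeros are kept: −(p_ALIS × m_ALIS − p_ELC × m_ELC)

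The documents give neither p nor m. Assumptions: m equal in both arms and between 20 and 40; p between 0% and 20%, higher on ALIS for illustration.

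| Zeros, ALIS vs ELC | Difference, zeros kept (m = 20 to 40) | Difference under the rule |
|---|---|---|
| 2% vs 0% | −0.4 to −0.8 | 0 |
| 5% vs 2% | −0.6 to −1.2 | 0 |
| 10% vs 5% | −1.0 to −2.0 | 0 |
| 20% vs 10% | −2.0 to −4.0 | 0 |

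For example, 10% vs 5% at m = 20 gives 0.90 × 20 − 0.95 × 20 = 18 − 19 = −1.0. In an arm of 50, 2% is one subject and 20% is ten; at 20% the arm mean is overstated by 0.2 × 20 = 4 to 0.2 × 40 = 8 points.

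The zeros in the last column follow from assuming equal m. These are also differences in raw means, whereas the plan fits a baseline-adjusted ANCOVA of change, so the table shows direction and order of size only.

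**The case against.** The case for leaving the rule alone has several parts.

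- **It is presented as an instrument scoring rule.** The SAP rests it on earlier validation work and calls a zero likely, not certainly, inaccurate. Some subjects may have COPD, and mild disease does not mean few symptoms. This stands in part: the rationale may fit some subjects, but the rule is applied to all of them and neither document argues it for MAC disease.
- **Subjects must be symptomatic at entry.** Protocol Section 4.1.1 requires respiratory signs or symptoms attributed to MAC and an average QOL-B respiratory score of at most 85. This stands for Baseline, where all-zero forms should be rare. A Day 1 zero need not lose the subject either, because SAP Section 7.3 takes the last non-missing value and Screening can serve. No such criterion applies at Month 7.
- **The size is assumed.** This stands. At the low end it is one subject in an arm of 50.
- **Little hangs on it.** This also stands. EXACT and E-RS comparisons sit under other efficacy assessments, SAP Section 7.2 makes all summaries descriptive, and the QOL-B respiratory and PROMIS fatigue endpoints have no such rule.

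A reader might infer that the rule also damages the psychometric validation, since EXACT and E-RS are concurrent validators. The documents do not support that. Protocol Section 10.5.2 places concurrent validity at Baseline, where zeros should be rare. Those analyses are governed by the Validation Analysis Plan, which is not among the documents, so whether the rule applies there is unknown.

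**Conclusion.** The point holds for the Month 7 EXACT total, E-RS total and E-RS subscales. The rule deletes the best attainable response on a rationale not shown to fit this population or visit schedule, and the available-data analysis does nothing to repair it. The treatment difference moves towards zero if all-zero forms are commoner in the better arm; if the rates are alike, the contrast is little affected. The illustrative 0.4 to 4 points depends wholly on the assumed zero rates, the assumed means of 20 to 40 and equal non-zero means, and the documents cannot narrow it.

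The mismatch between EXACT domains and E-RS subscales needs no assumption. It follows from the text and needs settling however rare zeros prove to be.

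It would go too far to say that every best outcome is deleted from both instruments: the EXACT domain scores carry no stated zero rule, and an E-RS total of 0 survives when items 12 to 14 are not all 0. Nor do the documents support reading this as a bias in the trial's main findings. It is a low-materiality, inexpensive correction.

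**What to change.** Amend SAP Sections 11.1.1, 11.1.2 and 11.1.5 as follows.

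1. At Month 7, analyse the EXACT total, E-RS total and E-RS subscales with all-zero forms kept as valid scores of 0.
2. Present the set-to-missing rule alongside as a sensitivity analysis.
3. Tabulate the number of all-zero EXACT forms by arm and visit. Careless completion can then be examined against the QOL-B, SGRQ and PGI-S answers from the same session, allowing for their different recall periods, instead of being presumed.
4. State one zero rule and apply it both to the EXACT domains and to the E-RS subscales.

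The cost is a change of wording, one extra table and a repeat of the Month 7 models. The downside is that the main summary departs from the COPD scoring convention; the sensitivity analysis keeps that version available for comparison with other studies.

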#### Domain scores

Three respiratory symptom domains are also embedded within the EXACT measure: Breathlessness, Cough & Sputum, and Chest Symptoms.

To compute domain scores, compute the raw domain score as the sum of the contributing domains first.

Item assignments to domains are as follows. Please note that items 4, 12, 13, and 14 do not correspond to a domain score and are not used in domain-specific analyses.

- Breathlessness: Items 7, 8, 9, 10, and 11
- Cough & Sputum: Items 2 and 3
- Chest Symptoms: Items 1, 5, and 6

For each raw domain score, the corresponding EXACT Domain score from [Table 5](#) is assigned. The EXACT Domain score has a theoretical range of 0 to 100, with higher

values indicating a more severe condition. Negative change from baseline indicates improvement (post therapy score – baseline score < 0).

**Table 4: Raw Summed Score to Scale Score Conversion Table for EXACT Total Score**

Raw Summed Score	EXACT Total Score	Raw Summed Score	EXACT Total Score
0	0	26	50
1	8	27	51
2	13	28	52
3	17	29	53
4	20	30	54
5	23	31	55
6	25	32	57
7	27	33	58
8	28	34	59
9	30	35	60
10	31	36	61
11	33	37	63
12	34	38	64
13	36	39	65
14	37	40	67
15	38	41	68
16	39	42	70
17	40	43	72
18	41	44	73
19	42	45	75
20	43	46	77
21	44	47	80
22	46	48	83
23	47	49	87
24	48	50	92
25	49	51	100

**Table 5: Raw Summed Score to Scale Score Conversion Table for EXACT Domains**

Domain Raw Summed Score	Breathlessness Domain Score	Cough & Sputum Domain Score	Chest Symptoms Domain Score
0	0	0	0
1	11	13	12
2	19	25	23
3	25	39	31
4	30	56	38
5	34	72	45
6	38	86	52
7	42	100	58
8	45		65
9	48		72
10	52		79
11	56		88
12	60		100

Domain Raw Summed Score	Breathlessness Domain Score	Cough & Sputum Domain Score	Chest Symptoms Domain Score
13	65		
14	71		
15	78		
16	87		
17	100		

### 11.1.2. EXACT RS™

The E-RS is an 11-item subset of the EXACT PRO assessing exacerbations of respiratory symptoms (Leidy, 2014a; Leidy, 2014b).

If missing values occur for individual items, the scores cannot be calculated and should be set to missing.

#### RS-Total Score

The RS-Total score is the sum of the individual raw item scores (item 1 to item 11) of the EXACT PRO (see [Appendix C](#)). Scores range from 0 to 40. Higher values indicate a more severe condition. Negative change from baseline indicates improvement (post therapy score – baseline score < 0).

#### E-RS: COPD Subscale Scores

For each subscale, the sum of the item-level scores across the items comprising the scale is calculated.

- RS-Breathlessness: Items 7, 8, 9, 10, 11 (score range 0–17)
- RS-Cough & Sputum: Items 2, 3, 4 (score range 0–11)
- RS-Chest Symptoms: Items 1, 5, 6 (score range 0–12)

If the EXACT total score is 0, the RS-Total Score and Subscale Scores will be set to missing.

### 11.1.3. SGRQ

The SGRQ is a self-administered instrument for the assessment of overall health, daily life, and perceived well-being among individuals with obstructive airway disease (Jones, 1992). The instrument consists of 50 items with 76 weighted responses grouped into a set of 17 questions. The items are divided into 2 parts and 3 categories: symptom, activity, and impact. Part 1 (symptom component) assesses an individual's perception of their recent respiratory problems. Part 1 evaluates frequency and severity of symptoms including cough, sputum production, wheezing, breathlessness, and the duration and frequency of attacks of breathlessness and wheezing. Part 2 (activity and impact components) addresses individuals' current state.

The responses to all questions must be mapped to weights as shown in [Appendix D](#) and [Appendix E](#).

The component scores are derived from the summed weights of the contributing questions (see below). After summation, the summed weights are normalized by the maximum possible sum of weights for each component.

$$\text{Score} = 100 * \frac{\text{Summed weights of responses in that component}}{\text{Maximum possible weights of responses in that component}}$$

If a response is missing, the weight of this response will not be counted in the denominator, i.e., in the *Maximum possible weight of responses in that component*.

The questionnaire contains questions allowing multiple responses. The manual refers to them as ‘questions’ (question 11-16), the eCRF calls them ‘Sections’ (Section 2-7).

Consistent with the instrument’s manual, the term ‘question’ is used below.

Lower values for the component scores indicate a better state of health. Negative change from baseline indicates improvement (post therapy score – baseline score < 0).

#### Symptoms component

This is calculated from the summed weights for the responses to questions 1-8. The maximum possible sum of weights is 662.5. The Symptoms component will tolerate a maximum of 2 missed responses.

If the subject had no severe attack in the past 4 weeks (ie, question 5 = ”none of the time”), question 6 cannot be answered. In this case, question 6 has a weight of 0 and is not considered missing.

#### Activity component

This is calculated from the summed weights for the positive responses to questions 11 and 15. As these questions are multiple choice, there is a total number of 16 responses in this component. The maximum possible sum of weights is 1209.1. The Activity component will tolerate a maximum of 4 missed responses.

#### Impacts component

This is calculated from the summed weights for the positive responses to questions 9, 10, 12-14, and 16-17. As questions 12-14 and 16 are multiple choice, there is a total number of 26 responses in this component. The maximum possible sum of weights is 2117.8. The Impacts component will tolerate a maximum of 6 missed responses.

If the subject did not receive respiratory treatment, question 14 cannot be answered. In this case, all responses to question 14 are considered FALSE even if they are missing on the eCRF. The responses are not missing for the calculation of the component score.

If the subject never held a job, question 10 cannot be answered. In this case, the response should be missing and will be considered missing for the component score.

#### Total score

This is calculated from the summed weight of all responses in the questionnaire. The maximum possible sum of weights is 3989.4. The total score will be calculated only if all component scores are calculated.

#### 11.1.4. FACIT-Fatigue

The FACIT-Fatigue Scale is a short, 13-item, easy to administer, tool measuring an individual's level of fatigue during their usual daily activities during the past week (Smith, 2010). FACIT-Fatigue is routinely administered in studies of respiratory disease populations for accurately evaluating the common sequelae of fatigue.

The FACIT-Fatigue score ranges from 0 to 52, with higher scores indicating a better quality of life. Positive change from baseline indicates improvement (post therapy score – baseline score > 0).

##### Item-level reversal

All item values except An5 and An7 must be reversed before further derivations (see Appendix F). The coding must be changed to show 0 = 'Very much' to 4 = 'Not at all'.

##### Fatigue Subscale Score

The Fatigue subscale score is the sum of the item scores. Missing items will be replaced by the mean of the answered items:

$$\text{Fatigue subscale score} = \frac{\text{Sum of item scores}}{\text{Number of items answered}} * 13$$

If less than 7 items are answered the subscale score is set to missing.

#### 11.1.5. Analysis of PRO Scores

PRO scores will summarize available data. Summaries will be presented by treatment group and by timepoint, as follows. Summaries will include:

1. Basic statistics of actual values and change from baseline to all protocol-specified timepoints.
2. LS-mean of change from baseline to Month 7, differences of LS-mean changes from baseline (ALIS + background regimen – ELC + background regimen) estimates and corresponding 95% CIs derived from ANCOVA model. The ANCOVA model will include change from baseline as response variable and treatment, baseline value, and history of MAC lung infection (initial or subsequent) as independent variables.

The following PRO scores will be summarized:

EXACT (see Section 11.1.1)

- EXACT Total score
- Breathlessness domain score
- Cough & Sputum domain score
- Chest Symptoms domain score

EXACT-RS (see Section 11.1.2)

- RS-Total score
- RS-Breathlessness subscale score

- RS-Cough & Sputum subscale score
- RS-Chest Symptoms subscale score

SGRQ (see [Section 11.1.3](#))

- Total score
- Symptom component score
- Activity component score
- Impact component score

FACIT – Fatigue Scale (see [Section 11.1.4](#))

- Fatigue subscale score

## 11.2. PGI-S

### 11.2.1. PGI-S Respiratory

The PGI-S Respiratory score is a categorical rating of symptom severity. The scale ranges from 1 = not at all to 5 = extremely severe ([Appendix G](#)). Negative change from baseline indicates improvement (post therapy score – baseline score < 0).

### 11.2.2. PGI-S Fatigue

The PGI-S Fatigue score is a categorical rating of symptom severity. The scale ranges from 1 = not at all to 5 = extremely severe ([Appendix G](#)). Negative change from baseline indicates improvement (post therapy score – baseline score < 0).

#### 11.2.2.1. Analysis of PGI-S Scores

Change from baseline to Month 7 in PGI-S scores will be analyzed similarly to QOL-B respiratory domain, see [Section 9.3.2.2](#) for details.

